#### **4.2 Dose Justification**

The recommended dosage of Voxelotor is 1500 mg taken orally daily, with or without food. The dose of voxelotor to be used in this study (weight-based 1500 mg equivalent) is based on clinical efficacy and safety results from voxelotor clinical studies in adult and adolescent participants combined with Pop PK modeling, physiologically based PK (PBPK) modeling, and allometric scaling. Dosing for participants <12 years of age will be weight based, as presented in **Table 1**, and is anticipated to provide exposures similar to adolescent participants receiving voxelotor 1500 mg. These doses are based on Pop PK and, PBPK modeling and allometric scaling and are expected to provide exposures of voxelotor equivalent to exposures observed in adults (Study GBT440-031) and adolescents (Studies GBT440-007 and GBT440-031)

**Table 1: Voxelotor Weight-based Doses for Participants Less than 12 Years of Age**

Population	Voxelotor Doses (1500 mg Equivalent)
10 to <20 kg	600 mg
20 to <40 kg	900 mg
≥40 kg	1500 mg

Participants will receive voxelotor administered orally daily as tablets (300 or 500mg) or dispersible tablets (100 mg and 300 mg each). All participants younger than 12 years of age will receive a dose based on their body weight to provide exposure corresponding to the adult dose of 1500 mg/day. Participants 12 years or older will take 1500 mg/day.

#### **4.3 Acquisition and Accountability**

All study drug packaging must be returned at each visit, regardless of whether they are empty or contain unused study drug (voxelotor). Unused tablets will be counted and recorded. Dates of receipt, dispense, return, lot numbers, and tablet counts will all be recorded in a log.

In accordance with GCP, the investigational site will account for all supplies of voxelotor drug product. Details of receipt, storage, assembly, and return will be recorded. The Investigator must ensure that all drug product supplies are kept in a secure locked area with access limited to those authorized by the Investigator.

The Sponsor Investigator (or designee) will maintain an accurate record of the receipt of voxelotor drug product as shipped by **GBT**, including, but not limited to, the date received, storage conditions/location, lot number, amount received, and the disposition of all voxelotor drug product.

Current dispensing records will also be maintained including the date and amount of voxelotor drug product dispensed and the participant receiving the drug product. This drug accountability record will be available for inspection at any time.

All unused supplies of voxelotor drug product will either be destroyed by the site or returned to the shipping depot at the end of the study.

#### **4.4 Formulation, Appearance, Packaging, and Labeling**

Voxelotor will be supplied as 300 or 500 mg tablets or as 100 mg and 300 mg dispersible tablets. Voxelotor dispersible tablets will be supplied in HDPE bottles with induction sealed polypropylene child-resistant caps.

Voxelotor tablets will be supplied in high-density polyethylene (HDPE) bottles with induction-sealed polypropylene child-resistant caps. Bottles and/or cartons will be labeled according to applicable regulations.

#### **4.5 Product Storage and Stability**

Voxelotor will be stored at controlled room temperature between 15 °C and 25°C (59°F to 77°F) in a secure, temperature-controlled and locked environment with restricted access at the Sponsor-Investigator's site. No special procedures for the safe handling of voxelotor are required.

#### **4.6 Preparation**

Voxelotor is a tablet ready to be swallowed. Voxelotor dispersible tablets should be dispersed in clear liquid (e.g., water, clear soda, apple juice, electrolyte drinks, flavored drinks, or sports drinks). Detailed instructions for study drug administration will be provided to participants and their caregivers/legal guardians, as needed.

#### **4.7 Study Intervention Compliance**

[figure not shown]
Study drug compliance will be assessed by counting of unused tablets or stick packs. In addition, medication compliance will be reported by the participant and caregiver.

#### **4.8 Concomitant Therapy**

A concomitant medication is defined as any prescription or over-the-counter preparation, including vitamins and supplements. All concomitant medications will be recorded in the participants medical record and the study case report form at study visits. Participants will be asked always to check with the PI or clinical study staff before taking a new medication. Prohibited medications include sensitive CYP3A4 substrates with a narrow therapeutic index and strong CYP3A4 inhibitors.

## 5. Procedures Involved

### 5.1 Study Schema

#### Study Population, N=50

- Age 4-30 years
- HbSS, S/ $\beta^0$  thalassemia
- Stable HU permitted
- No transfusion in prior 8 wks

#### Study Outcomes

- 1: Change in CBF, OEF, CMRO2 from baseline at 12 Weeks
- 2: Correlation between CBF, OEF and change in total Hb and Hb modification
- Exploratory: Correlation between CBF, OEF, CMRO2 and change in measures of RBC health

## 5.2 Schedule of Assessments (SoA)

FDNIRS/DCS and TCD measurements will be made on D1, or within the screening period depending on researcher availability. For the 4w, 8w, and 12w and end of study visits, the time point given spans a window of +/- 7 days. For patients continuing commercial voxelotor after 12w, the end of treatment (12w) visit will also serve as the end of study visit. Patients who will not continue commercial voxelotor after 12w will complete an end of study visit up to 8 weeks after last study dose.

	Screening (up to 28 days)	Treatment				End of Study (up to 8 wks post-treatment)
		D1 (+/- 7d)	4w (+/- 7d)	8w (+/- 7d)	12w (+/- 7d)	
Consent/Accent	X					
Inclusion/Exclusion Criteria	X					
Medical History & PE	X	X			X	
Height, weight	X				X	X
Vital signs, pulse oximetry	X	X	X	X	X	X
CBC diff, retic	X	X	X	X	X	X
CMP & LDH	X				X	X
Hb Electrophoresis	X				X	
Hb morphology	X	X	X	X	X	X
RBC Health		X			X	
FDNIRS/DCS (performed by [name] Lab staff)		X	X		X	
Transcranial Doppler ultrasound (TCD)	(X)	X			X	
Pregnancy testing (for females of child bearing potential)	X					
Adverse event reporting	X	X	X	X	X	X
Drug dispensing		X	X	X	X	

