## 2. Objectives and Endpoints

OBJECTIVES	ENDPOINTS	JUSTIFICATION FOR ENDPOINTS
Primary		
Evaluate the cerebral hemodynamic effects of voxelotor	Change in CBF, OEF and CMRO2 from baseline at Week 4 and 12	Voxelotor is a promising new drug that improves hemoglobin levels and reduces the incidence of worsening anemia in SCD. However, it is unclear whether this increase in hemoglobin is associated with reductions in blood flow and oxygen extraction in the brain
Secondary		
Evaluate the relationship between CBF, OEF, CMRO2 and change in total Hb levels	Correlation of CBF, OEF, CMRO2 and change in total Hb levels from baseline	By increasing hemoglobin levels, voxelotor may show improvement in CBF, OEF, CMRO2 akin to the effects of blood transfusion but without the detrimental side effects.
Evaluate the relationship between CBF, OEF, CMRO2 and voxelotor-modified Hb levels	Correlation of CBF, OEF, CMRO2 and level of RBC content of voxelotor-modified Hb	Voxelotor modification of Hb correlate to improvement of anemia. Quantified level of Hb modification (via HPLC or PK) may correlate with improvement in CBF, OEF, CMRO2
Exploratory		
Evaluate the relationship between CBF, OEF, CMRO2 and measures of RBC health	Correlation of CBF, OEF, CMRO2 and change in markers of RBC hemolysis (LDH, indirect Bil) and morphology (blood smear, RBC indices, retic, dense cells, and adhesion) from baseline	Restored RBC health is measured by reduction in hemolysis (measured by blood chemistry labs) and improvement in RBC morphology. Measured improvements in RBC health may correlate with

[figure not shown]
OBJECTIVES	ENDPOINTS	JUSTIFICATION FOR ENDPOINTS
		improvement in CBF, OEF, CMRO2

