## 5.3 Efficacy, Safety, and Other Assessments

Screening will occur up to 28 days prior to the start of the study. The subject's medical chart will be used for screening and for part of collection of trial data, per Health Insurance Portability and Accountability Act (HIPAA) rules, other relevant federal or state laws, and local institutional requirements, as applicable. Information obtained from the medical chart will include:

- a) List of current medications and their doses
- b) Vital signs

- c) Transfusion history
- d) Stroke history
- e) Previous MRI and/or MRA's
- f) Previous sleep studies
- g) Previous transcranial Doppler ultrasound results.

The study procedures and evaluations to be done as part of the study to support the determination of efficacy, as per the primary and secondary objectives outlined in this protocol, will include:

- **DCS/FDNIRS assessments.** Measurements of cerebral blood flow, oxygen extraction, and oxygen metabolism will be made by a trained study staff personnel using a customized diffuse correlation spectroscopy combined with frequency domain near infrared spectroscopy oximeter (Figure 2). A DCS/FDNIRS optical sensor will be manually held over the right and left forehead to obtain a brief (<1min) resting state measure of brain hemodynamics.

Measurements will be repeated up to 3 times per hemisphere (Figure 3). Total time of exam is typically 15-30 minutes. Measurements will be made before, and at 4 and 12 weeks after the start of voxelotor. Measurements will be obtained in quiet area of Aflac outpatient clinics using PPE and hand hygiene practices according to hospital policy.

- A research blood specimen will be obtained when a clinical sample is unavailable. Up to sixteen mLs of venous blood will be collected at each visit. Laboratory assessments relevant to measures predictive of voxelotor response and to measures of RBC Health will be performed at local (central CHOA lab) clinical labs. Local laboratory assessments will include complete blood count, reticulocyte count, hemoglobin electrophoresis, RBC dense cells and measures of RBC hemolysis (LDH, indirect bilirubin). RBC health laboratory assessments will include but are not limited to RBC adhesion.
- **Procedures that will be completed during the study as part of regular standard of clinical care:** These include physical examination, vital sign assessment (heart rate, blood pressure, pulse oximetry, etc.), medical history.

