## **17. Statistical Considerations, Data Management and Confidentiality**

### **17.1 Statistical Considerations**

#### **Statistical Hypothesis**

- Primary Endpoint: CBF and OEF are significantly lower at 4 and 12 weeks of treatment with voxelotor compared to pre-treatment levels. Paired t-test or Wilcoxon signed-rank test will be used to evaluate results, as patients are their own controls.
- Secondary Endpoints: The change in OEF and CBF from pre-treatment levels are significantly correlated with the change in hemoglobin. The change in OEF and CBF from pre-treatment levels are correlated with markers of hemolysis.

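### Baseline LDH and bilirubin are scheduled only at Screening and the baseline RBC Health sample only at D1, while the scan may fall at either, so one lab set can be up to 28 days out of step with the scan

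*Combined protocol and SAP*

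**What the plan says.** On the baseline scan, the text of Section 5.2 states: "FDNIRS/DCS and TCD measurements will be made on D1, or within the screening period depending on researcher availability". On the length of the screening period, Section 5.3 states: "Screening will occur up to 28 days prior to the start of the study". The Section 5.2 column header gives the same 28 days.

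The Section 5.2 grid marks the rows that matter as follows:

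| Row | Screening | D1 | 4w | 12w |
|---|---|---|---|---|
| CMP & LDH (source of LDH and bilirubin) | X | – | – | X |
| RBC Health | – | X | – | X |
| "CBC diff, retic" | X | X | X | X |
| Hb morphology | X | X | X | X |
| FDNIRS/DCS scan | – | X | X | X |

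The grid has no Screening mark for FDNIRS/DCS, although TCD has one in brackets. The option to scan during screening therefore rests on the text alone.

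These labs feed the correlation analyses. Section 2 lists as exploratory the correlation of the scan measures with "change in markers of RBC hemolysis (LDH, indirect Bil) and morphology (blood smear, RBC indices, retic, dense cells, and adhesion) from baseline". Section 17.1 lists under secondary endpoints: "The change in OEF and CBF from pre-treatment levels are correlated with markers of hemolysis". The Study Summary also places hemolysis and RBC health in the secondary objective, whereas the outcomes list in Section 5.1 places RBC health under exploratory.

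I found no definition of baseline, no rule that scan and blood draw share a day, and no limit on the interval between them.

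**The concern.** A correlation between change in brain measures and change in blood markers assumes that both changes start from the same point. Here the two baselines can come from different weeks. Any movement in LDH, bilirubin or adhesion between the two dates enters the lab change but has no counterpart in the scan change. If that movement is unrelated to the scan, it is noise and will tend to weaken the association.

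Two features make the baseline pair matter. CMP & LDH is not drawn at week 4, so each patient has only two scheduled scan/chemistry pairs, at baseline and week 12. RBC Health likewise has two. In addition, the acute-event and transfusion exclusions in Section 9.2 look back from the signing of consent, and the grid checks eligibility only at Screening. The fixed look-back windows therefore do not cover an event between Screening and D1.

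The study is a pilot meant to inform a larger trial. An association understated because of timing could be carried into that planning.

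**Working it through.** There is no stated power or sample-size figure to reproduce on this point. The check is of the intervals that the schedule permits.

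**Inputs (Sections 5.2 and 5.3).** Let d be the days from the Screening chemistry draw to D1, and s the days from the baseline scan to D1. Each may lie between 0 and 28.

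**Step 1: gap for each lab set.**
- LDH/bilirubin to scan: |d − s|.
- RBC Health to scan: s, because that sample is scheduled at D1.

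**Step 2: can both be zero?** Because |d − s| + s ≥ d, the two gaps always add up to at least d. Both vanish only if d = 0, that is, if Screening and D1 coincide.

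**Step 3: widest case, d = 28.**

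| Scan | LDH/bilirubin gap | RBC Health gap |
|---|---|---|
| On D1 (s = 0) | 28 days | 0 days |
| Mid-screening (s = 14) | 14 days | 14 days |
| Start of screening (s = 28) | 0 days | 28 days |

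The D1 column header carries a window of ±7 days. If that is read as lengthening screening, the maximum becomes 28 + 7 = 35 days. This is an assumption: the Section 5.2 text applies the window to the 4-, 8- and 12-week and end-of-study visits only, and Section 5.3 caps screening at 28 days.

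**Step 4: which markers are exposed?** LDH, indirect bilirubin and the RBC Health panel are exposed. Adhesion is the only item Section 5.3 names in that panel. Dense cells may be exposed too, but the documents do not make clear which grid row holds them. CBC, reticulocytes and Hb morphology are drawn at both pre-treatment visits, so a D1 scan has same-visit values for them.

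**Step 5: effect on a correlation (illustration only).** Suppose independent fluctuation over the gap has an SD of f times the SD of the true lab change. A change-score correlation r is then seen as r/√(1 + f²). For an assumed r of 0.50:
- f = 0.25: 0.50/√1.0625 = 0.485
- f = 0.5: 0.50/√1.25 = 0.447
- f = 1: 0.50/√2 = 0.354

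Both f and r are assumptions; the documents supply neither. Section 17.2 specifies a random-intercept mixed model on the values at weeks 0, 4 and 12, which also uses differences between patients. These figures show the likely direction and do not estimate the loss in that model.

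**The case against.** The strongest reply is that little of the analysis is exposed. Total hemoglobin is the correlate named for the leading secondary endpoint and the adjuster in the Section 17.2 primary analysis, and the CBC is drawn at both visits. The other Section 2 secondary endpoint concerns the level of voxelotor-modified Hb, which does not need a pre-treatment chemistry draw. The grid places the scan at D1, where RBC Health is a same-visit sample. The 28 days is a ceiling, and no expected Screening-to-D1 interval is given. Eligibility rules exclude patients with recent acute events, recent transfusion or an unstable hydroxyurea dose. Section 5.3 lets clinical samples supply labs, so same-day chemistry may sometimes exist. Section 17.2 calls the results descriptive.

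Most of this stands, and it rules out some stronger readings. A reader might infer that every correlation is weakened, or that the scan endpoint itself is compromised. The documents do not support that: the unadjusted paired scan comparison uses no lab value, and hemoglobin is out of step only if the wrong CBC is chosen or the scan falls on neither CBC date. A reader might also infer that baselines will typically be a month apart, but the documents set only the permitted maximum.

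The reply does not remove the core problem. Even with every scan at D1, the paired LDH and bilirubin come from Screening, and no rule limits how old they may be. The availability of clinical samples is not guaranteed.

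**Conclusion.** The point holds for the hemolysis markers (LDH, indirect bilirubin) and the RBC Health panel (at least adhesion). Following the schedule exactly leaves one of these sets out of step with the baseline scan by up to 28 days, unless Screening and D1 coincide. The gap exceeds 28 days only if the D1 window is read as extending screening.

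The consequence is avoidable noise in correlations that the documents call secondary in some places and exploratory in others. How much noise cannot be stated without within-patient variability data. The week-12 labs and scan share a scheduled visit, so no comparable gap is built in there, although no text requires the same day.

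Hemoglobin is a smaller matter of definition. Two pre-treatment CBCs exist and nothing says which is baseline, so the choice reaches the hemoglobin-adjusted primary analysis. This is a modest flaw, worth correcting because the remedy is cheap.

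**What to change.** - Add CMP & LDH to the D1 draw and keep the Screening draw for eligibility. A D1 scan then has all its labs at the same visit.
- Make a D1 scan before the first dose the preferred arrangement. It should not be mandatory, since that could lose baseline scans, and with them the primary endpoint, when the scan team is unavailable.
- If the scan is done in screening, draw CBC, CMP/LDH and the RBC Health sample at that visit where possible. Where this fails and the scan falls between the two chemistry draws, the nearer draw is at most 28/2 = 14 days away.
- Record the scan-to-draw interval for every patient, so that a sensitivity analysis can use it.
- Define baseline labs, including the hemoglobin used in the Section 17.2 adjustment, as the pre-dose values closest to the scan.
- Reconcile the Section 5.2 grid with its text on whether a screening scan is allowed, and state whether the D1 window extends screening.

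The cost is one extra chemistry assay at a visit where blood is already taken, and some lost scheduling flexibility. Section 5.3 sets the allowance: "Up to sixteen mLs of venous blood will be collected at each visit". No tube volumes are given, so the site should confirm that the added assay fits within it.

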## 5.3 Efficacy, Safety, and Other Assessments

Screening will occur up to 28 days prior to the start of the study. The subject's medical chart will be used for screening and for part of collection of trial data, per Health Insurance Portability and Accountability Act (HIPAA) rules, other relevant federal or state laws, and local institutional requirements, as applicable. Information obtained from the medical chart will include:

- a) List of current medications and their doses
- b) Vital signs

- c) Transfusion history
- d) Stroke history
- e) Previous MRI and/or MRA's
- f) Previous sleep studies
- g) Previous transcranial Doppler ultrasound results.

The study procedures and evaluations to be done as part of the study to support the determination of efficacy, as per the primary and secondary objectives outlined in this protocol, will include:

- **DCS/FDNIRS assessments.** Measurements of cerebral blood flow, oxygen extraction, and oxygen metabolism will be made by a trained study staff personnel using a customized diffuse correlation spectroscopy combined with frequency domain near infrared spectroscopy oximeter (Figure 2). A DCS/FDNIRS optical sensor will be manually held over the right and left forehead to obtain a brief (<1min) resting state measure of brain hemodynamics.

Measurements will be repeated up to 3 times per hemisphere (Figure 3). Total time of exam is typically 15-30 minutes. Measurements will be made before, and at 4 and 12 weeks after the start of voxelotor. Measurements will be obtained in quiet area of Aflac outpatient clinics using PPE and hand hygiene practices according to hospital policy.

- A research blood specimen will be obtained when a clinical sample is unavailable. Up to sixteen mLs of venous blood will be collected at each visit. Laboratory assessments relevant to measures predictive of voxelotor response and to measures of RBC Health will be performed at local (central CHOA lab) clinical labs. Local laboratory assessments will include complete blood count, reticulocyte count, hemoglobin electrophoresis, RBC dense cells and measures of RBC hemolysis (LDH, indirect bilirubin). RBC health laboratory assessments will include but are not limited to RBC adhesion.
- **Procedures that will be completed during the study as part of regular standard of clinical care:** These include physical examination, vital sign assessment (heart rate, blood pressure, pulse oximetry, etc.), medical history.
- **Transcranial Doppler ultrasound** assessment of blood flow velocity in the main feeding arteries. Measurements will follow standard clinical protocols that are outlined routine screening in children with sickle cell disease. Baseline TCD assessment may occur at screening or at D+1 visit prior to study medication.

[figure not shown]

Figure 2, Picture of portable NIRS/DCS instrumentation. The cart takes up a footprint of approximately 1.5ft x 3ft.

Figure 3, (a) Non-invasive FDNIRS/DCS sensor comprised of fiber optics embedded in a 3D printed holder. The top row of fibers are for FDNIRS and the bottom row are for DCS (b) Depth sensitivity of FDNIRS/DCS measurements in a representative 10 year old child. (c) Patient measurement with a similar hand-held FDNIRS/DCS sensor.

## 5.4 Adverse Events and Serious Adverse Events

### Definition of Adverse Events (AE)

Adverse event means any untoward medical occurrence associated with the use of Voxelotor or NIRS/DCS measurements of cerebral hemodynamics, whether or not considered intervention-related (21 CFR 312.32 (a)).

### Definition of Serious Adverse Events (SAE)

An adverse event (AE) or suspected adverse reaction is considered "serious" if, in the view of either the investigator or sponsor, it results in any of the following outcomes: death, a life-threatening adverse event, inpatient hospitalization or prolongation of existing hospitalization, a persistent or significant incapacity or substantial disruption of the ability to conduct normal life functions, or a congenital anomaly/birth defect. Important medical events that may not result in death, be life-threatening, or require hospitalization may be considered serious when, based upon appropriate medical judgment, they may jeopardize the participant and may require medical or surgical intervention to prevent one of the outcomes listed in this definition. Examples of such medical events include allergic bronchospasm requiring intensive treatment in an emergency room or at home, blood dyscrasias or convulsions that do not result in inpatient hospitalization, or the development of drug dependency or drug abuse.

